4.0 OVERVIEW OF STUDY DESIGN/INTERVENTION

4.1 Design

This is a pilot, single-institution study, wherein one group of 6 women ≥18 years of age with operable, ≥1.5 cm, histologically-confirmed, invasive carcinoma of the breast and no evidence of distant metastases, for whom surgery is planned, will be enrolled. The 6 participating women will be treated with ipilimumab, nivolumab and cryoablation of the dominant primary tumor prior to the planned surgery.

At the time of the initial MSKCC surgical consultation, potentially eligible candidates will be identified, informed consent forms provided, and surgery-related dates requested/set per standard-of-care. As soon as possible, potentially eligible patients will be evaluated by 1) the principal investigator ([name]), a designated consenting medical oncologist for a medical oncology assessment or the referring surgeon and 2) consenting professionals from radiology for assessment of amenability to cryoablation, if feasible. All available (per the standard of care) imaging (MMG +/- breast US +/- breast MRI) will be reviewed to determine eligibility for cryoablation and thus, study participation. Whenever feasible, the radiology evaluation will be arranged prior to the presurgical testing date so that baseline research bloods may be collected after the patient is confirmed eligible and together with the non-study presurgical bloods. Prior to protocol intervention, consent will take place at the first available appointment with a consenting professional.

Consenting, eligible women, with tumors amenable to MRI or US-guided cryoablation will be enrolled. All study interventions (including the cryoablation, ipilimumab/nivolumab administration, and imaging dates) will be defined by the pre-determined, non-study surgical date. **Research study appointments/interventions will not interfere with the planned, standard-of-care, surgery arrangements.**

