4.2 Intervention

During study intervention planning, the standard of care for patients with early stage primary breast cancer diagnosis and treatment of as well as the timing of the definitive surgery schedule will not be altered in any way for patients participating in this study. If a patient experiences side effects from intervention resulting in a delay of their planned surgery date, this will be a failure of the primary endpoint. The planned intervention of this study is to obtain image guided biopsies, percutaneous MRI or US guided breast tumor cryoablation, and ipilimumab/nivolumab administration.

Most patients will have an outside biopsy confirming the diagnosis of breast cancer at the time of the initial surgical consultation. However, because the cryoablation procedure will cause near complete tumor destruction (that in turn will cause immunologic effect and antitumor response), pre-cryoablation breast biopsies will be performed. At least three 18G MRI or US-guided core biopsies of the primary breast tumor will be obtained (together with core biopsies of any suspicious lymph nodes as clinically or radiographically indicated) if feasible. Two core breast specimens will be provided to the MSKCC Breast and Imaging Center (BAIC) pathology department for routine (standard of care) testing. Additional core biopsy specimens will be sent to the immune monitoring facility (IMF) for research purposes as detailed in section 12. If not all three core biopsies can be performed, this will not make the patient ineligible.

The MRI or US-guided biopsies will be performed by investigators from the Breast Radiology Service with the assistance of investigators from Interventional Radiology and Anesthesiology as needed. Image guided percutaneous cryoablation can be performed through a small nick making it a minimally invasive procedure that has been performed safely in cancer patients for many years. The cryoablation will be performed 7-10 days prior to the surgery date.

Ipilimumab and nivolumab are fully human, monoclonal anti-CTLA4 antibodies that have shown anti-tumor activity and are now US FDA approved for the treatment of patients with unresectable advanced melanoma (unresectable stage III or stage IV).

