7.0 RECRUITMENT PLAN

The Evelyn H. Lauder Breast Center, in the Breast and Imaging Center at MSKCC provides a large referral base, with approximately 2000 new breast cancer referrals each year, with the vast majority of these representing early stage diagnoses. In 2014, the last year for which we have complete data, 719 (41%) of the 1774 women undergoing surgery at MSKCC for resectable invasive breast cancer underwent total mastectomy (with 59% undergoing breast conserving surgery). We anticipate an average accrual rate of 2-3 patients per month with complete accrual of 6 patients within 2-3 months. At the time of the initial MSKCC surgical consultation, potentially eligible candidates will be identified, informed consent forms provided, and surgery-related dates requested/set per standard-of-care. As described in detail in Section 4.1, at the time of initial presentation in the surgery clinic, potentially eligible study candidates will be identified by the surgeon and referred for an appointment with the Principal Investigator ([name]) or a consenting medical oncologist and an appointment with consenting professionals from radiology, if feasible, to evaluate eligibility for cryoablation. Prior to protocol intervention, consent will take place at the first available appointment with a consenting professional.

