14.0 BIOSTATISTICS

Definitive surgery confers cure for many women with early stage breast cancer and it is therefore imperative that any experimental pre-operative therapeutic innovation not undermine the timing of curative-intent surgery. Consequently, the primary endpoint for this study is safety/tolerability, as defined by the number of patients who do not develop grade 3 or 4 adverse events that necessitates a delay in surgery. Therefore, if 5 or 6 of the 6 patients are without an AE necessitating delay in surgery, the regimen will be considered safe/tolerable for further study. The probability of observing 5 or 6 patients (out of 6) who for whom therapy is safe/tolerable is 0.53 if the true safety/tolerability rate is 0.75, 0.65 if the true safety/tolerability rate is 0.80, and 0.89 if the true safety/tolerability rate is 0.90. This rule is based on the time period from start of the investigation regimen to the date of surgery, which is estimated to be approximately 15 days. Safety data up to 12 weeks following surgery will also be evaluated and reported.

Study design and analysis of the data will be performed with the assistance of [name], Division of Epidemiology and Biostatistics.

This is a pilot study using innovative methods and if cryoablation and single-dose ipilimumab/nivolumab is deemed safe, will result in the design of a larger trial. As such, there is no formal statistical analysis or sample size calculation for this study. All analysis will be descriptive in nature and the sample size is dictated by drug availability and budget constraints.

We have several exploratory secondary analyses. As noted above, all analyses will be evaluated descriptively and graphically. Serum and tumor biomarker levels (including lymphocytes and DC's) and serum cytokines will be plotted over the study timepoints. The ratio of specific intra-tumoral and serum t cell populations (i.e. CD4+FOXP3+ T-regulatory cells (Tregs) to CD8+Effector cells) will also be plotted over study timepoints. Other endpoints that will be summarized descriptively include ALC, and absolute T cell count.

Estimated accrual will be approximately 2-3 patients per month, making targeted completion of accrual within approximately 2 to 3 months of the study initiation.

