16.2 Data and Safety Monitoring

The Data and Safety Monitoring (DSM) Plans at Memorial Sloan Kettering Cancer Center were approved by the National Cancer Institute in September 2001. The plans address the new policies set forth by the NCI in the document entitled "Policy of the National Cancer Institute for Data and Safety Monitoring of Clinical Trials" which can be found at:

<http://cancertrials.nci.nih.gov/researchers/dsm/index.html>. The DSM Plans at MSKCC were established and are monitored by the Office of Clinical Research. The MSKCC Data and Safety Monitoring Plans can be found on the MSKCC Intranet at: <http://mskweb2.mskcc.org/irb/index.htm>. There are several different mechanisms by which clinical trials are monitored for data, safety and quality. There are institutional processes in place for quality assurance (e.g., protocol monitoring, compliance and data verification audits, therapeutic response, and staff education on clinical research QA) and departmental procedures for quality control, plus there are two institutional committees that are responsible for monitoring the activities of our clinical trials programs. The committees: *Data and Safety Monitoring Committee (DSMC)* for Phase I and II clinical trials, and the *Data and Safety Monitoring Board (DSMB)* for Phase III clinical trials, report to the Center's Research Council and Institutional Review Board.

During the protocol development and review process, each protocol will be assessed for its level of risk and degree of monitoring required. Every type of protocol (e.g. NIH sponsored, in-house sponsored, industrial sponsored, NCI cooperative group, etc.) will be addressed and the monitoring procedures will be established at the time of protocol activation.

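### No pausing rule is tied to the 5-of-6 criterion, so up to four more women could be treated after it can no longer be met

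*Combined protocol and SAP*

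**What the plan says.** Section 4.1 fixes the number treated: "The 6 participating women will be treated with ipilimumab, nivolumab and cryoablation of the dominant primary tumor prior to the planned surgery". Section 14.0 judges the regimen acceptable "if 5 or 6 of the 6 patients are without an AE necessitating delay in surgery"; Sections 1.0 and 12.1 give the same threshold. Section 4.2 defines failure through side effects of the intervention "resulting in a delay of their planned surgery date, this will be a failure of the primary endpoint".

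Section 14.0 gives the chance of passing as "0.53 if the true safety/tolerability rate is 0.75", "0.65 if the true safety/tolerability rate is 0.80" and "0.89 if the true safety/tolerability rate is 0.90".

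On timing, Section 7.0 states: "We anticipate an average accrual rate of 2-3 patients per month". Section 4.2 places the drugs 8 to 15 days before surgery. Section 8.0 allows consent up to 28 days before the drugs.

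On stopping, Section 13.0 deals with withdrawal, removal and replacement of individual subjects. Section 16.2 describes the institution's monitoring system, names a DSMC for Phase I and II trials, and says that "monitoring procedures will be established at the time of protocol activation". No section contains an interim look, a staggering requirement, or a rule for pausing after one or two failures.

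**The concern.** The criterion tolerates one failure in six. Once two women have failed, the remaining outcomes cannot change the primary conclusion, yet the plan does not say what happens to women who are registered or about to be registered.

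Section 14.0 itself stresses that surgery cures many of these patients and that an experimental pre-operative treatment must not disturb its timing. A woman treated after the second failure runs that risk while contributing nothing to the decision the trial was set up to make.

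**Working it through.** **Inputs.** n = 6 (Section 4.1); pass if at least 5 successes (Section 14.0); true tolerability rates p = 0.75, 0.80 and 0.90 (Section 14.0); accrual 2–3 per month (Sections 7.0 and 14.0); drugs to surgery 8–15 days (Section 4.2); consent to drugs at most 28 days (Section 8.0). Assumptions: patients are independent with a common rate p; q = 1 − p.

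**Step 1: reproduce the plan's figures.** P(pass) = 6p⁵q + p⁶.
- p = 0.75: 0.3560 + 0.1780 = 0.534 (plan 0.53)
- p = 0.80: 0.3932 + 0.2621 = 0.655 (plan 0.65; the unrounded value is 0.6554)
- p = 0.90: 0.3543 + 0.5314 = 0.886 (plan 0.89)

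The plan's figures reproduce, apart from the last digit at 0.80.

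**Step 2: when does the second failure occur?** P(second failure is patient k) = (k − 1) q² p^(k−2), for k = 2 to 6.

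| p | k=2 | k=3 | k=4 | k=5 | k=6 | Sum |
|---|---|---|---|---|---|---|
| 0.75 | 0.0625 | 0.0938 | 0.1055 | 0.1055 | 0.0989 | 0.466 |
| 0.80 | 0.0400 | 0.0640 | 0.0768 | 0.0819 | 0.0819 | 0.345 |
| 0.90 | 0.0100 | 0.0180 | 0.0243 | 0.0292 | 0.0328 | 0.114 |

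Each sum equals 1 − P(pass). Every sequence that reaches a second failure already fails the rule, so pausing there leaves the pass probabilities unchanged.

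**Step 3: whom would a pause spare?** If the second failure is patient k and L further patients have been dosed by the time it is known, max(0, 6 − k − L) women are spared. At least one is spared when k ≤ 5 − L. Each cell gives P(at least one spared), then the expected number spared.

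| p | L = 0 | L = 1 | L = 2 |
|---|---|---|---|
| 0.75 | 0.367; 0.85 | 0.262; 0.48 | 0.156; 0.22 |
| 0.80 | 0.263; 0.59 | 0.181; 0.32 | 0.104; 0.14 |
| 0.90 | 0.082; 0.17 | 0.052; 0.09 | 0.028; 0.04 |

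The maximum of four needs the first two women both to fail and L = 0: probability 0.0625, 0.04 and 0.01.

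**Step 4: which L is realistic?** With a 30.4-day month, patients are 30.4/3 = 10.1 to 30.4/2 = 15.2 days apart. Over 8–15 days from drugs to surgery, 8/15.2 = 0.5 to 15/10.1 = 1.5 further patients would be dosed. L = 0 to 2 covers this range.

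**Step 5: does pausing registration alone suffice?** Consent to surgery can take up to 28 + 15 = 43 days. At the planned accrual that is 43/15.2 = 2.8 to 43/10.1 = 4.3 registrations, taking each patient as registered at consent. If registered women were still treated, three in the pipeline would leave only k = 2 as a case in which anyone is spared (0.06, 0.04 and 0.01), and four would leave none. The pause must therefore also cover registered but untreated patients.

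**The case against.** A reader might infer that the plan directs treatment to continue after a second failure. It does not. Section 14.0 says how the final result is judged and is silent on accrual, and a target of six is not an instruction to ignore failures. The DSMC or the investigator could halt the study. Section 16.2 leaves monitoring procedures to activation, and a trigger may exist there that these documents do not show. Section 17.2.1 requires serious adverse events to reach the drug supplier within 24 hours and recognises that a study can be halted for safety. That objection stands against the stronger reading. It does not fill the gap: none of these arrangements refers to a count of primary-endpoint failures, an AE can delay surgery without being serious, and accrual is expected to finish in 2 to 3 months with no DSMC review interval stated.

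The benefit is also modest, especially at a true rate of 0.90 and when patients overlap. That stands.

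A pause triggered by any AE that delays surgery could stop a trial that can still pass. Section 14.0 first defines the endpoint by grade 3 or 4 events and then refers to an AE of any grade; Sections 1.0 and 12.1 also give no grade, and Section 4.2 speaks of side effects. This stands too, and it is why the trigger must be tied to one reconciled definition.

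Finally, this is a descriptive pilot, and later patients would still inform the safety tables and tissue studies. That is a real cost, but it arises only after the regimen has failed its own criterion.

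**Conclusion.** The point holds as an omission. After a second failure the 5-of-6 criterion is out of reach, the plan states no pause, and up to four more women could be treated without any bearing on the primary conclusion. The documents do not support saying that the plan requires this, or that such exposure is likely.

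At the plan's own rates, the chance that a pause spares at least one woman runs from 0.37 (rate 0.75, no overlap) down to 0.03 (rate 0.90, two already dosed). These figures assume independent patients, a common rate, a fixed denominator of six, and a pause that also stops treatment of registered but untreated women. The fixed denominator is not secure, because Section 13.0 replaces patients who withdraw before completing all assessments and does not say whether one who has already failed is included. The change is worth making because it protects patients with curable disease at almost no cost; its absence is not a fatal flaw.

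**What to change.** Add to Section 14.0: *When a second patient meets the primary-endpoint failure definition, registration and the start of study intervention in registered but untreated patients are paused pending DSMC review, because 5 of 6 can no longer be reached. Patients already treated complete the planned follow-up.*

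Two clarifications are needed for that trigger to match the decision rule:
- Reconcile the failure definition across Sections 1.0, 4.2, 12.1 and 14.0, so that the event that counts towards the pause is the one that counts against the 5-of-6 criterion. The choice of definition is the sponsor's.
- State in Section 13.0 that a patient who has failed and then withdraws is not replaced in the denominator of six.

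If a trigger already exists in the activation-stage monitoring procedures, Section 14.0 should cite it and use the same definition.

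The cost is a short amendment. The pass probabilities do not change. The downside is fewer biomarker and late-safety observations, only in a trial that has already failed its rule.

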Ipilimumab is to be administered as an IV infusion with a 0.2 μ m or 1.2 μ m in-line filter using a volumetric pump, at the 1 mg/kg dose, to complete the infusion in 90 minutes with at least 10 cc normal saline flush at the end. The total dose needed should be prepared and administered per institutional guidelines. The total dose must be calculated using the most recent subject weight (obtained on the same day of, and prior to, the infusion).

Nivolumab is to be administered as an IV infusion with a 0.2 μ m or 1.2 μ m in-line filter using a volumetric pump, at the 3 mg/kg dose, to complete the infusion in 60 minutes with at least 10 cc normal saline flush at the end. The total dose needed should be prepared and administered per institutional guidelines. The total dose must be calculated using the most recent subject weight (obtained on the same day of, and prior to, the infusion).

Separate infusion bags and filters must be used for each infusion. Nivolumab is to be administered first. The nivolumab infusion must be promptly followed by a saline flush to clear the line of nivolumab before starting the ipilimumab infusion.

9.2 Pre-cryoablation core biopsies:

At least three 18G MRI or US-guided core breast biopsies will be obtained at the core biopsy appointment for all participants, if feasible. If not all three core biopsies can be performed, this will not make the patient ineligible. Core biopsies of clinically or radiographically suspicious lymph nodes will also be obtained as indicated. Two core breast specimens will be provided to the MSKCC BAIC pathology department for routine (standard of care) testing. Additional core biopsy specimens will be sent to the IMF for research purposes as detailed in section 12. The MRI or US-guided biopsies will be performed by investigators from the Breast Radiology Service with the assistance of investigators from Interventional Radiology and Anesthesiology as needed.

9.3 Cryoablation:

Percutaneous, MRI or US-guided cryoablation will be performed with a multiple freeze-thaw cycle. Freeze-thaw cycle strategies will be individualized to the patient and their tumor. Generally two cycles will be performed with each cycle being approximately 10 minutes of freeze time. Intermittent imaging will guide the procedure to ensure the ice ball does not encroach on critical structures, including skin. The number of probes used will depend on the lesion size and location.

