11.2 Infusion Reactions

Ipilimumab and/or nivolumab may induce infusion or hypersensitivity reactions. If such a reaction were to occur, it may manifest with fever, chills, rigors, headache, rash, pruritus, arthralgias, hypo or hypertension, bronchospasm, or other symptoms. Infusion reactions should be graded according to Common Terminology Criteria for Adverse Events (CTCAE, Version 4.0) guidelines. Treatment recommendations are provided below and may be

modified based on clinical judgment, local treatment standards and guidelines, and/or specific symptoms, as appropriate:

For Grade 1 symptoms: Mild reaction [e.g., localized cutaneous reactions including mild pruritus, flushing, rash] requires infusion rate to be decreased; intervention may be indicated.

- Decrease the rate of the study drug infusion until recovery from symptoms.
- Remain at bedside and monitor subject until resolution of symptoms. Diphenhydramine 50 mg may be administered at the discretion of the treating physician.
- When symptoms resolve, restart the infusion at the original infusion rate.

For Grade 2 symptoms: Moderate reaction [i.e., any symptom not listed above (mild symptoms) or below (severe symptoms) such as generalized pruritus, flushing, rash, dyspnea, hypotension with systolic blood pressure > 80 mm Hg], requires infusion interruption but responds promptly to symptomatic treatment [e.g., antihistamines, nonsteroidal anti inflammatory drugs, narcotics, corticosteroids, i.v. fluids]; prophylactic pre-infusion medications indicated for ≤ 24 hours.

- Discontinue the study drug infusion.
- Begin an i.v. infusion of normal saline, and treat the subject with diphenhydramine 50 g i.v. (or equivalent) and/or paracetamol 325 to 1000 mg (acetaminophen).
- Remain at bedside and monitor subject until resolution of symptoms. Corticosteroid therapy may be administered at the discretion of the treating physician.
- When symptoms resolve, restart the infusion at 50% of the original infusion rate; if no further complications ensue after 30 minutes, the rate may be increased to 100% of the original infusion rate.
- Monitor subject closely. If symptoms recur, immediately discontinue the infusion; no further study drug will be administered at that visit. Administer diphenhydramine 50 mg i.v., and remain at bedside and monitor the subject until resolution of symptoms.
- The amount of ipilimumab infused must be recorded.

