For Grade 3 or Grade 4 symptoms: Severe reaction [e.g. bronchospasm, generalized urticaria, systolic blood pressure < 80 mm Hg, or angioedema], Grade 3: prolonged [i.e. requiring 6 or more hours to respond to symptomatic medication and/or discontinuation of infusion]; recurrence of symptoms following initial improvement; hospitalization indicated for other clinical sequelae [e.g., renal impairment, pulmonary infiltrates].

Grade 4: life-threatening; pressor or ventilatory support indicated.

- Immediately discontinue the study drug infusion. No further study drug will be administered. The amount of study drug infused must be recorded on the case report form (CRF).
- Begin an i.v. infusion of normal saline, and treat the subject as follows: Recommend bronchodilators, epinephrine 0.2 to 1.0 mg of a 1:1,000 solution for subcutaneous administration or 0.1 to 0.25 mg of a 1:10,000 solution injected slowly for i.v.

Memorial Sloan Kettering Cancer Center

IRB Protocol #: 16-495 A(5)

Approved: 3-MAY-2017

administration, and/or diphenhydramine 50 mg i.v. with methylprednisolone 100 mg i.v. (or equivalent), as needed.

- Remain at bedside and monitor subject until recovery from symptoms.
- Subject should be monitored until the treating physician is comfortable that the symptoms will not recur.
- Treating physician should follow their institutional guidelines for the treatment of anaphylaxis

In the case of late-occurring hypersensitivity symptoms (e.g., appearance of a localized or generalized pruritus within 1 week after treatment), symptomatic treatment may be given (e.g., oral antihistamine or corticosteroids).

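### Section 13 replaces women who withdraw without excepting withdrawal because of toxicity, so a treated woman can leave the 5-of-6 safety count and a failing 4 of 6 can become a passing 5 of 6

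*Combined protocol and SAP*

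**What the plan says.** All references are to the combined protocol and SAP.

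- **Endpoint and rule.** Section 14 defines the primary endpoint as "the number of patients who do not develop grade 3 or 4 adverse events that necessitates a delay in surgery" and states that "if 5 or 6 of the 6 patients are without an AE necessitating delay in surgery, the regimen will be considered safe/tolerable". The rule covers the time from the start of the regimen to surgery, estimated at about 15 days. Section 4.2 gives the matching failure event: side effects "resulting in a delay of their planned surgery date, this will be a failure of the primary endpoint".
- **Population.** Section 12.1 evaluates safety in all treated subjects.
- **Removal and replacement.** Under Section 13 a woman may withdraw at any time, may be removed for severe unacceptable side effects, and is removed if she does not have the planned surgery at the centre. Anyone who withdraws after consent but before all study assessments are complete is replaced. Assessments run well past surgery: research blood about 30 days after it, and safety visits until at least 12 weeks after dosing (Section 1, Appendix 1).
- **Infusion stops.** Section 9.1.2 says "Nivolumab is to be administered first". For a Grade 3 or 4 reaction, Section 11.2 says "Immediately discontinue the study drug infusion. No further study drug will be administered". For Grade 2 it says "If symptoms recur, immediately discontinue the infusion; no further study drug will be administered at that visit", and Appendix 1 has a single dosing visit. These steps may be "modified based on clinical judgment, local treatment standards and guidelines". Under Grade 2 the recording instruction is "The amount of ipilimumab infused must be recorded"; the Grade 3 or 4 text asks for the amount of study drug.

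**The concern.** The rule has a fixed denominator of six, but no text says which six once someone has been replaced. Section 13 makes replacement depend on withdrawal alone, whatever the reason. The women most likely to withdraw after dosing include those with a troublesome adverse event, who are also the women most likely to have surgery delayed. Dropping them and enrolling someone else removes failures selectively.

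The replacement window is also much longer than the endpoint window. A woman whose surgery was delayed, and who withdraws some weeks later, has a known primary outcome but still meets the condition for replacement.

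The rule decides whether the regimen goes forward to a larger trial in women who can be cured by surgery alone. With six women, one change in the count can reverse that decision.

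**Working it through.** **Inputs.** n = 6 and a pass at 5 or more (Section 14). True success rates p = 0.75, 0.80 and 0.90 (Section 14). Women are taken as independent. The documents give no rate of AE-related withdrawal, so the share w below is an assumption.

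**1. The plan's own figures.** P(X ≥ 5 | 6, p) = 6p⁵(1−p) + p⁶ = 0.534, 0.655 and 0.886. The plan states 0.53, 0.65 and 0.89. They reproduce (0.65 is 0.655 truncated).

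**2. The count itself.** Two failures among six give 4 of 6: not safe. If one of the two withdraws because of her adverse event and is replaced, the verdict depends on the replacement. It becomes 5 of 6 with probability p, that is 0.75, 0.80 or 0.90, where it should have been zero. The chance of exactly two failures is 15p⁴(1−p)² = 0.297, 0.246 and 0.098.

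**3. Average effect.** Suppose a share w of would-be failures withdraw and are replaced until six women remain, successes do not withdraw, and replacements have the same p. Each retained woman is then a success with probability s = p / [p + (1−p)(1−w)], and the pass chance is P(X ≥ 5 | 6, s).

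| p | w = 0 | w = 0.10 | w = 0.25 | w = 0.50 |
|---|---|---|---|---|
| 0.75 | 0.53 | 0.58 | 0.66 | 0.79 |
| 0.80 | 0.66 | 0.70 | 0.76 | 0.86 |
| 0.90 | 0.89 | 0.90 | 0.93 | 0.96 |

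For example, p = 0.75 and w = 0.25 give s = 0.75 / (0.75 + 0.25 × 0.75) = 0.80, so the rule behaves as if the true rate were 0.80. The effect is larger where the regimen is less safe.

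**4. Given one AE-related withdrawal whose on-time surgery cannot be confirmed.** If she is replaced, the pass chance is that of six fresh women: 0.53, 0.66 and 0.89. If she counts as a failure, all five others must succeed: p⁵ = 0.24, 0.33 and 0.59.

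**5. A woman stopped during nivolumab who stays on study and has surgery on time.** She is a treated subject and no adverse event delayed surgery, so Sections 4.2, 12.1 and 14 together make her a success. The rule then passes if at least 4 of the other 5 succeed: P(X ≥ 4 | 5, p) = 0.63, 0.74 and 0.92. No withdrawal is involved, and Section 13 does not replace her for incomplete dosing.

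**The case against.** **All treated subjects are evaluated, so nobody is lost.** Section 12.1 does say this, and the adverse event would be tabulated and seen; in a descriptive study of six women it would hardly be overlooked. That stands for safety reporting. It does not settle the 5-of-6 count, because with a replacement there are more than six treated women and no rule for choosing among them. If the sponsor already intends to keep such women in the count, the fix only writes that down.

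**Withdrawals will be rare.** The treatment is a single dose followed by surgery within about two weeks, so this may well be so. The documents give no rate. With no AE-related withdrawal, nothing changes.

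**Removal is not withdrawal.** This is correct. Section 13 attaches replacement only to withdrawal and does not say how a woman removed by the investigator, or removed for not having the planned surgery, is scored or whether she is replaced. The bias is explicit for withdrawals; for removals the text is silent.

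**A stronger reading concerns incomplete dosing.** A reader might infer that the rule is wrong because a woman who gets part of the nivolumab and no ipilimumab can count as tolerating the whole regimen, and that she should be a failure. The documents do not support this. Section 14 gives its reason: pre-operative treatment must not disturb the timing of curative surgery, and the endpoint follows from that. No text makes a stopped infusion a failure, so setting p⁵ against the step 5 figures for her would test a rule the plan does not contain. Failing a recurrent Grade 2 reaction would also go below the Grade 3 or 4 threshold in Section 14. What remains is a limit on interpretation: she provides little evidence about the combination.

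**Conclusion.** The concern holds for replacement. As written, Section 13 allows a treated woman who withdraws because of an adverse event to leave the primary count, and the resulting bias is towards a finding of safe. One such replacement can turn 4 of 6 into 5 of 6. On average, if 10% to 50% of would-be failures were lost this way, the pass chance would rise from 0.53 to between 0.58 and 0.79 at a true rate of 0.75, and from 0.89 to between 0.90 and 0.96 at 0.90. These figures rest on independence, on withdrawal only among would-be failures, and on an assumed share that the documents do not supply.

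The point is minor: it matters only if such a withdrawal occurs, and the event would still be visible in the safety tables. It would be wrong to infer that 0.53, 0.65 and 0.89 are mistaken, or that scoring a stopped infusion with on-time surgery as a success is an error. The former are correct for the endpoint as defined, and the latter follows from a deliberate choice of endpoint.

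**What to change.** - **Sections 13 and 14.** Keep the surgery-delay endpoint. Keep every woman who starts study drug in the primary count, apart from the non-AE withdrawals below, and score her on whether an adverse event necessitated a delay. Count as a failure any woman who withdraws or is removed because of an adverse event before on-time surgery can be confirmed. Replace only women who withdraw before any study drug, or who withdraw before surgery for a reason unrelated to an adverse event. Once surgery has taken place, replace nobody.
- **Reporting.** Beside the primary result, list for each woman the delivered dose of each drug and whether cryoablation was done. Report infusion stops for reactions separately.
- **Section 11.2, Grade 2.** Record the amount of each study drug infused, since nivolumab runs first. Leave the reaction-management steps as they are.

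**Cost.** A few sentences, one wording edit and one listing. There are no extra patients, since replacement becomes narrower than it is now. The rule becomes stricter if an AE-related withdrawal occurs: given one scored as a failure, the pass chance at a true rate of 0.90 is 0.59 instead of the 0.89 under replacement. It may occasionally fail a woman whose surgery would have been on time, which is why the failure applies only where this cannot be confirmed.
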